9.4 Permanent Discontinuation in Response to Adverse Events

Grade 1 or 2

In general, a participant who develops a Grade 1 or 2 AE as defined by the DAIDS Table for Grading Adult and Pediatric Adverse Events, Version 1.0, December 2004 (Clarification dated August 2009) regardless of relationship to study medication will continue study medication use.

Grade 3

For participants who develop a Grade 3 AE as defined by the DAIDS Table for Grading Adult and Pediatric Adverse Events, Version 1.0, December 2004 (Clarification dated August 2009) that is judged by the study investigators to be unrelated to study medication, the study medication will continue. The study medication must be permanently discontinued for participants who develop a Grade 3 AE judged by a physician investigator to be related to the study medication.

Grade 4

If a participant develops a Grade 4 AE as defined by the DAIDS Table for Grading Adult and Pediatric Adverse Events, Version 1.0, December 2004 (Clarification dated August 2009) and the AE is determined to be related to study medication, then study medication must be permanently discontinued.

Any time a participant is permanently discontinued from study medication (prior to completion of the 12 week course of study medication), HCV resistance testing will be performed.

9.5 HIV-1 Infection

Participants who are positive for HIV (known or positive at Screening) will not be eligible to participate. If HIV seroconversion occurs during the time of study medication use, the study medication will continue.

9.6 Criteria for Early Termination of Study Participation

Participants may voluntarily withdraw from the study for any reason at any time. The study investigators also may withdraw participants from the study to protect their safety and/or if they are unwilling or unable to comply with required study procedures. Participants also may be withdrawn if Gilead Sciences, government or regulatory authorities, including the FDA and Office for Human Research Protections (OHRP), or site IRBs/ECs terminate the study prior to its planned end date. Detailed reason for the withdrawal of a participant will be documented in the research record. Every reasonable effort will be made to continue to follow the participant as scheduled for safety.

10 STATISTICAL CONSIDERATIONS

10.1 Overview and Summary of Design

This is a Phase 1, single-arm, open label study of treatment for chronic HCV infection during pregnancy in 10 HCV-infected pregnant women with a 12-week course of SOF/VEL.

10.2 Study Endpoints

Pregnant women meeting all of the criteria in section 5.2 and 5.3 will be enrolled into the study and followed prospectively through 12 weeks after the last dose of study medication. Infants will be enrolled upon delivery and followed prospectively through approximately one year of age.

10.2.1 Primary Endpoints: Maternal

The primary endpoints of the study are primary plasma PK parameters (specifically AUC_{tau} , C_{max} , and C_{min}) of VEL, SOF, and GS-331007 assessed at 3 weeks (+/- 7 days of medication initiation).

10.2.2 Secondary Endpoints: Maternal

The secondary endpoints of the study are:

- 1) Secondary plasma PK endpoints of VEL, SOF and GS-331007:
 - a. Free-fraction of VEL, SOF and GS-331007
- 2) Secondary PK endpoints for intracellular SOF (GS-461203)
 - a. Pre-dose GS-461203 concentrations from dried blood spots and peripheral blood mononuclear cells
- 3) Maternal sustained virologic response after 12 weeks of therapy (SVR12)
- 4) Adverse events including clinical and laboratory changes
- 5) Pregnancy outcomes including the following:
 - a. delivery prior to 37 completed weeks of gestation
 - b. stillbirth or intrauterine fetal demise
 - c. intrapartum hemorrhage
 - d. postpartum hemorrhage
 - e. non-reassuring fetal status
 - f. chorioamnionitis
 - g. hypertensive disorders of pregnancy
 - h. gestational diabetes
 - i. intrauterine growth restriction

10.2.3 Exploratory Endpoints

The exploratory endpoint of the study is:

- 1.) In depth interviews conducted before enrollment in screened participants and after completion of treatment in enrolled participants.

Secondary Endpoints: Infant

Consistent with the secondary study objectives, the following secondary endpoint will be assessed for infants:

- Major malformations, defined as structural abnormalities with surgical, medical, or cosmetic importance.
- Weight, length, and head circumference at birth, 8 weeks, six months and 12 months.
- Neurodevelopmental assessments at 6 months and 12 months as measured by Bayley Scales of Infant and Toddler Development and Ages and Stages Questionnaire (ASQ).
- Perinatal HCV transmission assessed by presence of HCV RNA at 8 weeks, six months or 12 months.

10.3 Sample Size

To evaluate the primary objective, we estimate a desired sample size of 10 participants. In order to maintain our sample size, any participant who discontinues treatment during the 12-week treatment period will be replaced. Based on SOF/VEL prescribing information, we will have 87% power to detect a 50% decrease in VEL AUC and >99% power to detect a 2-fold increase. For power calculations we chose this degree of change in VEL AUC because the therapeutic range of SOF/VEL is quite wide and decreases in VEL AUC of up to 50% and increases of up to 2-fold are still associated with efficacy and have acceptable safety/tolerability, respectively.

The FDA does not recommend co-administration of VEL with EFV because it decreases the VEL AUC by >50% [34]. Additionally, this sample size provides an estimated power of 0.82 to detect a 25% change in the AUC of the SOF, given the reported interpatient variability of 35.6% among female patients. Power determinations were performed in SAS v. 9.4 (SAS, Cary, NC).

Any participant that discontinues the study before the PK3 visit is completed or if a participant reports missing more than 1 dose per week averaged over the duration of the study then they will be replaced by recruiting another participant into the study.

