Preliminary data: Our Phase 1 trial of ledipasvir/sofosbuvir (LDV/SOF) treatment in pregnancy has promising preliminary results. Between June 2017 and October 2018, 9 pregnant women between 23-24 weeks' gestation with chronic genotype 1 HCV infection were treated with LDV 90mg- SOF 400mg daily for 12-weeks. Three intensive PK visits were performed at 25-26, 29-30, and 33-34 weeks' gestation. Plasma was collected pre-dose, 0.5, 1, 2, 3, 4, 5, 8 and 12 hours post-dose to measure LDV, SOF and GS-331007 (the inactive metabolite of SOF) by

validated HPLC-MS/MS methods²⁸. Of 29 women screened, 20 were excluded due to genotype 2 or 3 infection (n=10), ongoing illicit drug use (n=4), declining participation (n=3), intention to deliver off-site (n=2), and an APRI score of >1 (n=1). All 9 women enrolled were white, with a median age of 31 years. Our published data documented that 93% of pregnant women having HCV at our institution are white²⁹. Eight women were HCV infected due to intravenous drug use (4 receiving opioid pharmacotherapy) and one was perinatally infected. All nine (100%) participants were cured and there were no adverse events greater than grade 2 related to LDV/SOF³⁰. There were no significant differences found between the PK parameters at each gestational age timepoint.

Although there are significant physiologic differences between pregnant and non-pregnant women, there are minimal differences between the second and third trimesters of pregnancy³¹. For example, the glomerular filtration rate is increased 37% in the second trimester and 40% in the third trimester³². Therefore, PK parameters were averaged across the three visits and compared between participants and non-pregnant women from regulatory trials of LDV/SOF. The geometric mean ratios and corresponding 90% confidence intervals are shown in Table 1. *Similar LDV and SOF, but lower GS-331007 exposures were observed between pregnant and non-pregnant women. All nine participants (100%) were cured. There were no adverse events related to LDV/SOF greater than grade 2. One-year follow-up of infants is on-going, and all remain HCV negative.*

Table 1: Sofosbuvir, GS-331007, and Ledipasvir Exposure in HCV-Infected Pregnant women Compared to Non-Pregnant Women

PK Parameter Mean (%CV)		HCV-infected Pregnant Women (N=8)**	HCV-infected Non-Pregnant Women (N=43)***	%GMR (90%CI)
SOF	AUC _{tau} (hr*ng/mL)	1840 (15.2)	2210 (49.9)	92.0 (78.8, 107)
	C _{max} (ng/mL)	1290 (29.3)	1640 (47.8)	89.0 (68.6, 115)

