10.5 Data Analysis

10.5.1 Analysis of SOF and VEL concentrations

Between-group comparisons will evaluate changes in SOF and VEL PK parameters between the historical controls (nonpregnant women without severe renal disease or cirrhosis) compared to the 10 pregnant women. Area under the time concentration curve over a dosing interval (AUC_{tau}), maximum concentration (C_{max}), and minimum concentration (C_{min}) will be calculated, as applicable. The PK parameters (including the free-fraction of VEL and intracellular SOF concentrations) of the pregnant women will be compared to the historical control group by calculating the geometric mean ratios and 90% CIs. Drug concentrations will be summarized descriptively (mean, median, minimum, maximum, standard deviation) by study visit.

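### The power figures in section 10.3 do not match the planned geometric-mean-ratio analysis: 87% and >99% cannot both hold for VEL, and 0.82 for SOF fits a 25% decrease but not a 25% increase

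*Combined protocol and SAP*

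**What the plan says.** Section 10.3 (Sample Size) is the only quantitative support for the sample size: "we estimate a desired sample size of 10 participants". For VEL it states "we will have 87% power to detect a 50% decrease in VEL AUC and >99% power to detect a 2-fold increase", with the source given only as "Based on SOF/VEL prescribing information". For SOF it states "this sample size provides an estimated power of 0.82 to detect a 25% change in the AUC of the SOF". The only variability figure in the section belongs to that SOF statement and reads "given the reported interpatient variability of 35.6% among female patients". The section gives no VEL variability, significance level, sidedness, test, scale of analysis or number of historical controls.

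Section 10.5.1 sets the analysis: the PK parameters of the pregnant women "will be compared to the historical control group by calculating the geometric mean ratios and 90% CIs". The pilot study of ledipasvir/sofosbuvir, tabulated in section 2.2, was reported in the same way.

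**The concern.** A geometric mean ratio with a 90% CI is a difference of mean logs, and asking whether the interval excludes 1 is a two-sided 10% test. Changes by the same factor up and down are then equally far from no effect. Halving and doubling should have the same power, yet 10.3 gives 87% and >99%. A 25% fall and a 25% rise are not the same factor, so they should have different power, yet 10.3 gives one figure for both.

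Section 10.3 treats halving as the limit for retained efficacy and doubling as the limit for acceptable tolerability, so a reader needs a reliable power for each. The SOF sentence also implies a sensitivity to increases that the planned comparison may not have.

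**Working it through.** **Inputs.** From 10.3: n1 = 10; VEL ratios 0.5 and 2; SOF change 25%; SOF CV 35.6%. From 10.5.1: log scale and 90% CI, hence two-sided alpha 0.10. The number of controls n2 is not stated. I use 43 as a low assumption, the size of the pilot's comparison group in section 2.2 ("HCV-infected Non-Pregnant Women (N=43"), then 200, and 1000 as a near-unlimited group.

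**Formulas.** Log SD s = √ln(1 + CV²); standardised shift d = |ln ratio| / s; noncentrality = d / √(1/n1 + 1/n2); power from the noncentral t with n1 + n2 − 2 degrees of freedom.

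**Reproducing the stated figures.** The nearest single basis for all three is an arithmetic-scale, one-sided 10% test:
- SOF: d = 0.25/0.356 = 0.702, power 0.76 to 0.82 (43 to 1000 controls).
- VEL: 87% for halving needs a CV of 0.59 to 0.65, and doubling then exceeds 0.999.

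That basis is not stated in 10.3 and is not the analysis in 10.5.1.

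**VEL on the planned scale.** |ln 0.5| = ln 2 = 0.693. The shift is the same, so the power is the same whatever s, alpha and n2 are. Solving for the CV that gives each stated power in both directions, at two-sided 10%:

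| Controls | CV for 87% | CV for 99% |
|---|---|---|
| 43 | 0.80 | 0.52 |
| 200 | 0.90 | 0.58 |
| 1000 | 0.93 | 0.59 |

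No single CV serves both figures. At two-sided 5% the corresponding ranges are 0.70 to 0.80 and 0.48 to 0.54, again without overlap. Equal variances in the two groups are not required. A Welch-test simulation (100,000 runs, CV 90% against 50%, 10 against 43) gave 0.817 for halving and 0.816 for doubling.

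**SOF on the planned scale.** s = √ln(1 + 0.356²) = 0.345. Decrease: d = |ln 0.75|/0.345 = 0.288/0.345 = 0.833. Increase: d = ln 1.25/0.345 = 0.223/0.345 = 0.646. At two-sided 10%:

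| Controls | 25% decrease | 25% increase |
|---|---|---|
| 43 | 0.757 | 0.568 |
| 200 | 0.820 | 0.634 |
| 1000 | 0.835 | 0.651 |

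So 0.82 is reached for the decrease with about 200 controls. The increase that has the same power is 1/0.75 = 1.33, a 33% rise. At two-sided 5% neither direction reaches 0.82 (at most 0.745, for the decrease). At one-sided 10% the 25% increase still reaches only 0.71 to 0.77.

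**The case against.** The best reply is that 10.3 names no scale, so the figures may be correct on an arithmetic one. As shown above, a one-sided 10% arithmetic test gives roughly all three. That makes the fault a mismatch between 10.3 and 10.5.1 rather than a slip in computation. This stands as an explanation of how the figures may have arisen. It does not rescue them, because they then describe a test the plan does not use.

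The VEL symmetry also has a condition: the log variance must not depend on the direction of the shift. If the arithmetic SD stayed constant instead, power would differ. With a control CV of 60% and a two-sided 10% log-scale Welch test, simulation gave 0.91 for halving and >0.99 for doubling. Constant CV is the more usual assumption in PK, and nothing in the plan indicates otherwise.

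For SOF, the table of possible pregnancy effects in section 2.2 shows no upward arrow, so a reader might take the change to be a decrease, where 0.82 is attainable. The wording is undirected, however, and even the decrease reaches 0.82 only with a control group of about 200, a number the plan does not give.

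Finally, the consequence for VEL may be favourable. If 87% came from the arithmetic one-sided basis, the planned analysis has 0.97 to 0.98 power in both directions; if from an arithmetic two-sided one, above 0.99. This is fair, and it is why the point is not that 10 women are too few for VEL. Nor does 10.5.1 state a null hypothesis or decision rule; the two-sided 10% level is inferred from its 90% CI.

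**Conclusion.** The concern holds: the power statement is wrong as written for the planned analysis. The two VEL figures contradict each other on the log scale, whatever the CV, alpha or number of controls, given a log variance that does not depend on direction. Which one is wrong cannot be determined without the VEL CV. For SOF, 0.82 describes a 25% decrease with about 200 controls; a 25% increase has about 0.57 to 0.65. The SOF sizes rest on the stated CV of 35.6%, the two-sided 10% level implied by the 90% CI, and assumed control numbers of 43 to 1000. This should be fixed, but it does not show that the sample size is inadequate.

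**What to change.** Recompute the power on the log scale at two-sided alpha 0.10 and replace the power sentences in 10.3. Suggested wording:

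> Power refers to log-transformed AUC, two-sided alpha 0.10, with 10 pregnant women and [N] historical controls. VEL (CV [x]%, [source]): power [p] for either a halving or a doubling. SOF (CV 35.6%, [source]): power [p1] for a 25% decrease and [p2] for a 25% increase.

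With 200 controls, p1 and p2 would be 0.82 and 0.63. Alternatively, keep 0.82, label it as power for a 25% decrease (equivalently a 33% increase), and state the number of controls; the VEL pair would still have to become one figure.

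The cost is one rewritten paragraph. Participants, endpoints and analysis are unchanged. The only drawback is that the SOF figure for an increase becomes less favourable, about 0.63 instead of 0.82 with 200 controls.

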10.4 Participant Accrual and Retention

Pregnant and chronically HCV-infected women who meet the criteria outlined in Section 5 and are interested in participating, will be enrolled into this study. Once a participant is enrolled, the study staff will make every reasonable effort to retain her for the entire study period. Any participant lost to follow-up prior to Visit 7 will be replaced.

10.5 Data Analysis

10.5.1 Analysis of SOF and VEL concentrations

Between-group comparisons will evaluate changes in SOF and VEL PK parameters between the historical controls (nonpregnant women without severe renal disease or cirrhosis) compared to the 10 pregnant women. Area under the time concentration curve over a dosing interval (AUC_{tau}), maximum concentration (C_{max}), and minimum concentration (C_{min}) will be calculated, as applicable. The PK parameters (including the free-fraction of VEL and intracellular SOF concentrations) of the pregnant women will be compared to the historical control group by calculating the geometric mean ratios and 90% CIs. Drug concentrations will be summarized descriptively (mean, median, minimum, maximum, standard deviation) by study visit.

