VEL bioavailability is estimated to be 30-50% based on animal studies and is not influenced by food intake. Notably, VEL requires an acidic environment for absorption. VEL is >99.5% protein bound, is hepatically metabolized by cytochrome P450 enzymes (CYP3A4, CYP2B6, and CYP2C8). VEL is primarily eliminated via biliary excretion, resulting in a plasma half-life of 15 hours^{33,34}. The bioavailability of SOF is >80% and a high fat meal increases SOF exposure by 67-91%. SOF is 61-65% plasma protein bound, 14% is hepatically metabolized by phosphorylation, and 80% is renally excreted. As a prodrug, SOF half-life is 0.4 hours, while GS-331007 is 27 hours. SOF is administered as a phosphoramidate prodrug of the uridine nucleotide analogue GS-331007 monophosphate³⁵. SOF is hydrolyzed by cathepsin A and/or carboxyesterase 1 and then phosphorylated by cellular kinases to the triphosphate moiety (GS-461203)^{35,36}. GS-461203 is the active form of SOF. GS-461203 then is dephosphorylated to GS-331007, which is the inactive SOF metabolite that is most readily measured in the plasma.

The physiologic changes of pregnancy and the possible PK effects on SOF and VEL are shown in Table 1.

Table 1. Possible Impact of Pregnancy on VEL and SOF PK				
	Physiologic Alteration in Pregnancy	VEL	SOF	Comment
Absorption	Increased gastric pH	↓	--	Acid reducing agents decrease VEL levels
	Nausea and vomiting	↓	↓	Decreased absorption of both VEL and SOF
	Slowed gastrointestinal motility	--	--	Decreased Cmax and increased Tmax
Distribution	Volume expansion	--	--	VEL and SOF are only slightly soluble in water
	Reduced protein binding	↑	--	Increased free fraction of VEL (highly bound)
Metabolism	Hormone-mediated enzyme alterations	↓	?	Upregulation of CYP3A, no data on SOF enzymes
Excretion	Cholestasis due to estrogen	↑	--	Reduced biliary excretion of VEL
	Increased renal blood flow	--	↓	Increased excretion of SOF

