4.2 Summary of Major Endpoints

Primary Endpoint:

- **Systemic PK**
 - Systemic exposure of both VEL and SOF will be assessed at three time points:
 - 1) 3 weeks after treatment initiation (intensive sampling);
 - 2) 6 weeks after treatment initiation (sparse sampling);
 - 3) 9 weeks after treatment initiation (intensive sampling).

Secondary Endpoints:

- **Secondary PK endpoints:**
 - Intracellular concentrations of GS-461203 from dried blood spots and peripheral blood mononuclear cells (PBMCs) will be assessed at:
 - 3 weeks \pm 7 days after first dose;
 - 6 weeks \pm 7 days after first dose;
 - 9 weeks \pm 7 days after first dose.
 - Free-fraction of VEL (protein-binding) will be assessed at:
 - 3 weeks \pm 7 days after first dose;
 - 9 weeks \pm 7 days after first dose.
- **Sustained Viral Response (SVR12)**

- HCV RNA viral load will be assessed at 12 weeks after SOF/VEL treatment completion. An undetectable viral load will be considered a SVR12.
- **Maternal Safety**
 - Safety laboratory assessments of blood counts, creatinine, liver function, creatinine kinase and lipase will be measured at the PK1 and PK2 visit (3 and 6 weeks after initiation of SOF/VEL).
 - Pregnancy and delivery outcomes collected prospectively by participant interview and medical record review.
- **Neonate Safety**
 - Major malformations, defined as structural abnormalities with medical, surgical or cosmetic importance
 - Weight, length, and head circumference at birth, 8 weeks, six months and 12 months
 - HCV RNA will be assessed at birth (as available), 1-3 months and 6 months, and then again at 12 months only if detectable viral loads are documented in either of the two previous viral load assessments
 - Neonatal development assessed at 6 months and 12 months

Exploratory Endpoint:

- In depth interviews conducted before enrollment in screened participants and after completion of treatment in enrolled participants

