the PK visits. Participants will be instructed about dietary restrictions for these visits as outlined in section 7.6. Participants will have their first PK plasma drawn before the time of the dose of SOF/VEL. The dose at each PK visit will be timed and blood samples will be collected at each PK visit as follows (relative to the timed dose): pre-dose, 0.5, 1, 2, 3, 4, 5, 8, and 12. An intravenous catheter may be placed and used to obtain samples throughout the PK visits. A saline solution will be used at a slow drip to attempt to keep the vein patent. In the event that the catheter fails, participants may have another IV inserted or individual venipuncture(s) to attempt to collect all PK samples. If still in place, the catheter will be removed after the 12 hour time point. If a PK sample(s) cannot be obtained, then the participant will remain evaluable, if at least one sample is obtained at each PK visit. Participants will return the following day for the 24 hour PK time point, which will be obtained by a single venipuncture. The participant will be instructed to take their daily dose following the single blood sample collection. For further details, see section 7.6 Pharmacokinetics.

For the sparse PK visit (PK2), the time when the previous dose of SOF/VEL was taken will be recorded and a single PK sample will be collected. This draw can occur at any time during the PK2 visit window and at any time during the day.

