7.6 Pharmacokinetics

All enrolled participants will undergo intensive serum PK specimen collection procedures at the PK1 and PK3 visits. These collections will occur at study visits as described in Table 9.

Table 9: SOF and VEL PK Sampling

Time since SOF/VEL*	Plasma Sample	Timed Meal	SOF/VEL PK sample (mL)	Protein Binding (mL)	PBMC/DBS sample (mL)	Total blood (mL)
predose	+		4	0	4	8
DOSING		+				
30 mins	+		4	0	0	4
1 hour	+		4	0	0	4
2 hours	+		4	6	0	10
3 hours	+		4	0	0	4
4 hours	+		4	0	0	4
5 hours	+		4	0	0	4
8 hours	+		4	0	0	4
12 hours	+		4	0	0	4
24 hours	+		4	0	0	4

*Time listed is the target time for PK sample. If a sample is collected prior to next scheduled PK sample it will not be considered a protocol deviation. Only missed samples will be considered protocol deviations.

Participants will be instructed to bring their daily dose of SOF/VEL to the visits requiring intensive PK sampling (PK1 and PK3 visits) for timed administration. If they do not bring their dose, then a dose of study medication can be dispensed from the pharmacy/PoR/designee. Intravenous catheters may be placed during intensive PK visits. A pre-dose sample will be collected. Study drug will be administered as close as possible to the participant's normal dose time if possible and within 5 minutes of completing and within 30 minutes of initiating a standardized moderate-fat-calorie breakfast (~600 calories and 25 to 30% fat) following an overnight fast (no food or liquids, except water, for at least 8 hours). Participants will be restricted from food intake until after collection of the 4 hour blood draw and restricted from water consumption 1 hour before and 2 hours after dosing, except for approximately 240 mL of water given with study drug and standardized meal. Whole blood will be collected into appropriate sized Vacutainer® Plus plastic sterile tube(s) with K₂EDTA (spray dried) additive. Immediately after collection, the collection tube will be inverted 8 to 10 times to allow mixing with the anticoagulant. Further processing instructions can be found in the Specimen Collection and Procedures Manual.

For the PK2 visit (sparse PK visit), a single 8mL blood sample (PK and PBMCs) will be drawn noting the time of the collection and the time at which the participant took their previous SOF/VEL dose.

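### Week-6 plasma concentrations come from one sample at any time after dose and are summarised by visit without using the recorded time since dose, so they do not measure exposure

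*Combined protocol and SAP*

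**What the plan says.** The Protocol Summary lists plasma exposure to VEL, SOF and GS-331007 at weeks 3, 6 and 9 under the primary endpoint. Section 4.2 does the same for VEL and SOF, including "6 weeks after treatment initiation (sparse sampling"). Section 10.2.1 is narrower: the primary parameters (AUCtau, Cmax, Cmin) are "assessed at 3 weeks (+/- 7 days of medication initiation").

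At the week-6 visit (PK2), section 7.4.1 says that "a single PK sample will be collected", and adds: "This draw can occur at any time during the PK2 visit window and at any time during the day". Section 7.6 has staff draw the sample "noting the time of the collection and the time at which the participant took their previous SOF/VEL dose".

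Section 10.5.1 calculates AUCtau, Cmax and Cmin where they apply and compares PK parameters with historical controls by geometric mean ratio. For concentrations it says: "Drug concentrations will be summarized descriptively (mean, median, minimum, maximum, standard deviation) by study visit". It gives no adjustment for time since dose, no model-based use of the sparse sample, and no rule for values below the assay limit.

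On half-lives, section 2.2 gives 15 hours for VEL and says: "As a prodrug, SOF half-life is 0.4 hours, while GS-331007 is 27 hours".

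**The concern.** One sample cannot give AUCtau or Cmax by non-compartmental methods, and an untimed sample is not Cmin. The by-visit description is therefore all that section 10.5.1 offers for week-6 plasma. It combines values from whatever points in the dosing interval the women happened to attend, so the result partly reflects clinic timing. Placed beside weeks 3 and 9, a high or low week-6 figure could be taken for a gestational change. For parent SOF, the summary could mix near-peak values with values below the assay limit.

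This point concerns plasma only. It does not address the intracellular GS-461203 endpoint.

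**Working it through.** The plan gives no figure for the week-6 summary, so there is nothing to reproduce. The question is how much draw time alone moves a value.

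**Inputs from the documents.** Half-lives are 15 h (VEL), 27 h (GS-331007) and 0.4 h (SOF), from section 2.2. The dosing interval is 24 h (section 6.1). SOF Cmax is 1290 ng/mL in pregnant and 1640 ng/mL in non-pregnant women, and SOF AUCtau in pregnant women is 1840 h·ng/mL. These SOF values come from the earlier LDV/SOF study tabulated in section 2.2 and serve as a proxy. There are 10 women.

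**Assumptions, not in the documents.** VEL Tmax 1-4 h; SOF Tmax 1 h; SOF assay limit 1-10 ng/mL.

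**1. Range for one woman, draws spanning the interval.** Under simple decline, fold change = 2^(time difference / half-life).
- VEL, 2 h versus 24 h: 2^(22/15) = 2.76.
- GS-331007, 2 h versus 24 h: 2^(22/27) = 1.76.
- A steady-state one-compartment oral model for VEL gives peak/trough ratios of 2.86, 2.69, 2.50 and 2.32 for Tmax of 1, 2, 3 and 4 h.

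**2. Range for VEL if every draw falls 1-10 h after dose.** The same model gives 1.50, 1.41, 1.31 and 1.32.

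**3. Added spread.** For draw times uniform over a window of W hours, the log-scale SD under simple decline is (ln 2 / half-life) × W / √12.
- VEL, W = 24: 0.0462 × 24 / 3.464 = 0.320. Geometric CV = √(exp(0.320²) − 1) = 33%. The one-compartment model gives a CV of 25-31%.
- GS-331007, W = 24: 0.0257 × 24 / 3.464 = 0.178, a geometric CV of 18%.
- Contribution to the standard error of a 10-woman geometric mean for VEL: 0.320 / √10 = 0.10, roughly 10%.
- VEL, draws at 1-10 h (W = 9): log SD 0.120, and 0.120 / √10 = 0.038, about 4%.

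These standard errors treat draw times as independent between women. If most women attend at a similar time after dose, the whole summary shifts, and the number of women does not reduce that shift.

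**4. Parent SOF.** Hours measurable = Tmax + half-life × log2(Cmax / limit). Two half-lives are used: the stated 0.4 h, and the slower value implied by AUC/Cmax, ln 2 × 1840 / 1290 = 0.99 h.

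| Half-life | Cmax and limit (ng/mL) | Hours measurable | Share of 24 h below limit |
|---|---|---|---|
| 0.4 h | 1290, 10 | 1 + 0.4 × 7.01 = 3.8 | 84% |
| 0.4 h | 1640, 1 | 1 + 0.4 × 10.68 = 5.3 | 78% |
| 0.99 h | 1290, 10 | 1 + 0.99 × 7.01 = 7.9 | 67% |
| 0.99 h | 1640, 1 | 1 + 0.99 × 10.68 = 11.6 | 52% |

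Across these cases SOF is below the limit for about 50-85% of the interval.

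**The case against.** The strongest reply is that nothing primary depends on week 6. Section 10.2.1 takes the primary parameters from week 3, section 2.2 presents sparse sampling as a way to limit burden, and no visit-to-visit test is planned. This stands and limits the weight of the point. It does not explain why the Protocol Summary and section 4.2 list week 6 under the primary endpoint.

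Second, draws may not span the interval. Section 6.2 prefers early-morning dosing and asks women to bring the dose to clinic only for PK1 and PK3, so many PK2 draws would follow a dose taken at home. In the 1-10 h window the VEL effect is modest. At the 0.99 h half-life, SOF would be measurable until 7.9-11.6 h, which covers most or all such draws. This also stands: the larger figures are conditional. But the protocol permits draws at any time, including just before the day's dose.

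Third, the plan also reports median, minimum and maximum. None of these accounts for time since dose.

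Two stronger readings are tempting and should not be made. A reader might set the near-3-fold VEL spread against the 2-fold AUC change in section 10.3. That would compare two single draws at opposite ends of the interval with a change in group AUC, and the power calculation does not use week 6. A reader might also infer that the intensive-visit time points will be averaged into one figure per visit. Section 10.5.1 does not say so, and it does not rule out tabulation by time point within a visit.

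Finally, matching to PK1 and PK3 is imperfect. Those visits have an observed dose after a fast and a standard breakfast (section 7.6); PK2 relies on the noted time of the previous dose. Section 2.2 says food does not influence VEL but that a high-fat meal raises SOF exposure by 67-91%. The remedy must allow for this.

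**Conclusion.** The concern holds as a limited, inexpensive improvement. The stated week-6 summary is confounded by draw time:
- **VEL:** up to about 2.3- to 2.9-fold for an individual value if draws span the interval, and about 1.3- to 1.5-fold if all fall 1-10 h after dose. Uniform draws over 24 h add a CV of about 25-33%, or roughly 10% standard error on a 10-woman geometric mean.
- **GS-331007:** up to about 1.8-fold, with an added CV of about 18%.
- **Parent SOF:** below the limit for about 50-85% of the interval, so a week-6 summary is not an exposure measure. This rests on an assumed assay limit and Tmax, on Cmax from the earlier LDV/SOF study, and on which half-life is used.

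It would be wrong to conclude that the primary analysis is undermined, since the week-3 parameters come from intensive sampling. Nor can one say without qualification that week-6 SOF will be mostly unmeasurable, because that depends on when the women are seen.

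**What to change.** In section 10.5.1:
- Replace the by-visit summary of week-6 VEL and GS-331007 with a within-woman ratio. Divide each week-6 concentration by the same woman's week-3 and week-9 concentrations, interpolated at the same recorded time after dose. Report geometric mean ratios with 90% CIs, labelled descriptive.
- Flag draws in the absorption phase, where PK2 lacks the observed dose and standard meal of PK1 and PK3 and interpolation is least reliable.
- List week-6 parent SOF individually by time since dose, marking values below the assay limit, with no summary statistic.

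In the Protocol Summary and section 4.2, remove parent SOF from the week-6 exposure endpoint and reconcile both with section 10.2.1 on which visits are primary.

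No new samples or visits are needed, because dose and draw times are already recorded. The cost is SAP wording, a small calculation, and the loss of a week-6 summary figure for parent SOF.
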